12. MEDICAL HISTORY

Medical History information will be summarised for the SCR and RND set, including both prior and concomitant events collected at Visit 1.

Medical History will be coded using the version of Medical Dictionary for Regulatory Activities (MedDRA) available at the time of the analysis and will be presented by SOC (System Organ Class) and PT (Preferred Term).

13. MEDICATIONS

Only medications administered to treat an AE or MDI will be collected and will be considered all concomitants.

Therapies will be presented for the SAF set and coded using Anatomical Therapeutic Chemical (ATC) Classification System.

14. STUDY MEDICATION EXPOSURE

Not applicable.

Document:	Y:\Kimberly-Clark\DryNites\Documentation\SAP\DryNites_SAP_v1.0_20200203		
Author:	[name]	Version Number:	1.0
		Version Date:	03Feb2020
Template No.: F	RWI_TP_BIOS0013 Revision 1		Reference: RWI_WI_BIOS0015
Effective Date:	15Jun2018		

15. Primary Outcome

Direct- to-patient data will be analysed descriptively at each assessment along with applicable change from baseline on the RND and PAS.

15.1 Primary Analysis

The primary analysis will be performed separately for age groups for the PAS comparing the 95% CI for the difference between the means of average wet nights at the end of intervention period for the 2 groups with the predefined margin. Being the primary analysis focused on last week of the intervention period (lasting from randomisation to Visit 3) and the equivalence margin reported as 2/7 (two nights over a week), the average number of wet nights was chosen as reliable outcome on primary endpoint.

15.1.1 Primary Analysis Variable & Derivation

The primary analysis variable will be the difference between the 2 groups on the average number of wet nights in Week 4 of the intervention study period and will be derived using the item "Did the child have an NE (nocturnal enuresis) event?" collected on daily diary. The number of "Yes" for each patient will be counted over the last 7 days of the intervention period (from randomisation till the Visit 3 day).

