8.3 Missing Data

Should missing data occur, the data will be analysed as recorded in the electronic CRF (eCRF), that is, analyses will be performed on patients with non-missing values. However, the amount of missing values for data elements will be reported, and the likely impact of missing data on the analysis and the pattern of the missing information will be assessed.

Depending upon the amount of missing data, and whether there is evidence of bias in the missing data (e.g., differences between patients with and without missing data), multiple imputation (detailed in Section 15.1.2), may be performed and a sensitivity analysis will be carried out comparing the results from the complete case analysis (where records with missing data will be dropped) and the full set analysis including the imputed data.

Missing safety data will not be imputed. Partial date handling is described in Appendix 2.

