15.1.2 Missing Data Methods for Primary Analysis Variable

Multiple imputation technique will be used to address missing values for primary endpoint in case of percentage of missing data will be $\geq 20\%$. Multiple imputation it's superior to single imputation in reducing statistical bias by building in random error into the imputation. This prevents underestimation of the degree of variability in the data, which affects the estimate of the standard error.

Document:	Y:\Kimberly-Clark\DryNites\Documentation\SAP\DryNites_SAP_v1.0_20200203		
Author:	[name]	Version Number:	1.0
		Version Date:	03Feb2020
Template No.:	RWI_TP_BIOS0013 Revision 1	I	Reference: RWI_WI_BIOS0015
Effective Date:	15Jun2018		

The following steps will be used:

- Differences on all key and outcome variables between patients with missing versus nonmissing values will be described and tabulated.
- Missing data will be imputed using SAS PROC MI under the assumption that the missing values are missing at random (MAR). This assumption requires that missing values be related to measured covariates, with no unmeasured related covariates.
- Results will be aggregated across the multiply imputed data sets using SAS PROC MIANALYZE.

The multiple imputation model will include the primary outcome as the number of wet nights during the last week on the 4 weeks period after randomisation, randomisation group, average number of wet nights during the run-in period, age and sex. The number of imputation data sets to be created is 100.

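### SAP 15.1.1 counts 'Yes' diary answers over seven days but does not say how an unanswered night counts or when a partly answered week is missing

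*SAP*

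**What the plan says.** The diary item on bed-wetting takes Yes or No each morning (Protocol 4.7.2), so an unanswered night is neither. SAP 15.1.1 takes the number of 'Yes' answers, which "for each patient will be counted over the last 7 days of the intervention period (from randomisation till the Visit 3 day". That is the only derivation of the primary variable. SAP 15.1 then compares the "difference between the means of average wet nights at the end of intervention period for the 2 groups with the predefined margin", but gives no rule for turning a part-filled week into an average.

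The missing-data text works per patient. SAP 8.3 analyses what was recorded, "that is, analyses will be performed on patients with non-missing values", and describes a "complete case analysis (where records with missing data will be dropped". SAP 15.1.2 adds "Multiple imputation technique will be used to address missing values for primary endpoint in case of percentage of missing data will be" 20% or more, and "Differences on all key and outcome variables between patients with missing versus nonmissing values will be described and tabulated". Neither section says how many answered nights make a week non-missing. SAP 7.3 only sets the diary cut by visit date.

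Protocol 5.4.5 leaves the detail of missing-data handling to the SAP. The SAP does give completeness rules for the questionnaires (15.2.1.2 and 15.2.2), including prorating once more than half the items are answered. It gives none for the diary.

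**The concern.** Two readings are open, and they lead to different trials.

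(a) *Literal count.* A blank adds nothing, so it scores as a dry night. In an equivalence trial, equal blanks in both arms pull the observed difference towards zero, which favours the sponsor's hypothesis. Unequal blanks bias it in either direction. Blanks also add variation between children, which costs power.

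(b) *Incomplete week is missing.* A child with one blank night loses the whole week. The six answered nights are discarded and cannot help the imputation, whose model holds, besides the weekly outcome, only "randomisation group, average number of wet nights during the run-in period, age and sex".

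The choice also decides whether the 20% trigger is reached. If the SAP does not settle it, it will be settled in programming, in an open-label trial whose primary analysis may run before database lock (SAP 5.2). Protocol 5.4.6 itself warns that incomplete diaries could leave a significant amount of missing data.

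**Working it through.** **Inputs from the documents.** Seven nights per child; wet-night probability 0.95 continuing and 0.80 discontinuing; margin 2/7, taken as 2 nights of 7; two-sided 95% CI; 15 continuing and 30 discontinuing per age group (Protocol 5.1, 5.2; SAP 8.1). I show 15/30 because SAP 15.1 states "The primary analysis will be performed separately for age groups for the PAS", and 30/60 because SAP 15.1.3 and Protocol 5.4.2 make the comparison across age groups and then by age. Both sizes are before the recruitment allowance.

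**Assumptions.** Blank rate m per night (10% in the main case); wetness independent between nights; blanks unrelated to wetness, either independent or clustered within child (beta-binomial, ICC 0.5); Satterthwaite CI; 20,000 simulations per cell.

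**The plan's own figure.** Protocol 5.2 states 99% power with 15/30. Repeating its simulation gives 97.7% with a Wald interval on pooled nights and 97.3% with an unequal-variance t interval. It reproduces to within 2 points, but every simulated child has seven answered nights.

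**Reading (a), expected bias.** The expected count is 7 x p x (1 - m). At the margin, p is 0.95 and 0.95 - 2/7 = 0.6643.
- No blanks: 7 x (0.95 - 0.6643) = 2.00 nights.
- 10% blank in both arms: 2.00 x 0.9 = 1.80.
- 10% pants, 5% no pants: 7 x (0.95 x 0.90 - 0.6643 x 0.95) = 1.57.
- 5% pants, 10% no pants: 7 x (0.95 x 0.95 - 0.6643 x 0.90) = 2.13.

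**Chance of declaring equivalence at a true 2-night difference** (clustered blanks in brackets)

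| Rule | Blanks, pants/no pants | 15/30 | 30/60 |
|---|---|---|---|
| Any | none | about 2% | about 2% |
| (a) count | 10/10 | 7% (2%) | 12% (5%) |
| (a) count | 10/5 | 22% (7%) | 44% (18%) |
| (a) count | 5/10 | 0.8% (0.3%) | below 1% |
| (b) complete weeks | 10/10 | about 2% | about 2% |
| wet/answered, at least 4 of 7 | 10/10 | about 2% | about 2% |

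**Power at 0.95 versus 0.80**

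| Rule | Blanks, pants/no pants | 15/30 | 30/60 |
|---|---|---|---|
| Any | none | 97% | above 99% |
| (a) count | 10/10 | 90% (53%) | above 99% (87%) |
| (b) complete weeks, not imputed | 10/10 | 70% (91%) | 96% (99.8%) |
| wet/answered, at least 4 of 7 | 10/10 | 95% (95%) | above 99% |

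A pooled-variance interval shows the same pattern for the count at 15/30: 1.1% false equivalence with no blanks, 5.2% at 10% in both arms.

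**The 20% trigger.** At 10% blanks, the share of children with any blank is 1 - 0.9^7 = 52% (23% clustered). The share with fewer than 4 answers is 0.3% (8%). With the trigger counted in children, it is met under the first definition of a missing week and not under the second.

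**The case against.** A reader might infer that the SAP commits to scoring blanks as dry, so that false equivalence is inflated several-fold. The documents do not support that. A pure count always exists, even for an empty week, so no child could ever be missing; that would leave SAP 8.3, 15.1.2 and 15.1.4 with nothing to act on. Read as a whole, the SAP expects some primary values to be missing, which fits (b) better, and under (b) false equivalence stays near 2% when blanks are random. The text still does not exclude (a) for a partly answered week.

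Other points stand. The largest figures need more blanks in the pants arm; the reverse imbalance is conservative, and no document suggests either direction. With clustered, equal blanks at 15/30 the count shows almost no inflation. The 70% power under (b) is for one age group before the 15 extra recruits in Protocol 5.2; if all of them were available (20/40, an upper bound) it would be about 83% (97%). A count over seven answered nights needs no divisor, so the gap is the handling of blanks and not the word 'average'.

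Blanks may also be few. Randomisation needs seven wet nights confirmed from the diary (Protocol 4.7.3), diaries are reviewed at visits, and the diary form and data management plan, which might prevent blanks, are not in the file.

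**Conclusion.** The omission is certain: the stated derivation does not cover an unanswered night, and nothing elsewhere in either document does. Its size is not certain, because it depends on the reading adopted and on blank rates that the documents do not give. On the better-supported reading, dropping incomplete weeks, the cost is power: material within an age group and small in the pooled comparison. On the literal reading the equivalence conclusion itself can be biased, towards equivalence if blanks are equal and either way if they are not. The documents do not support presenting the 7% to 44% figures as what the plan will do; they show what the unresolved wording allows under assumed blanks. This should be fixed before the analysis, with medium confidence in its practical impact.

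**What to change.** In SAP 15.1.1, define each child's value as 7 x wet nights / answered nights over the last 7 days of the intervention period, with a pre-specified minimum number of answered nights. Four of seven is one example, in line with the more-than-half rule the SAP uses for questionnaires. A minimum of five gives similar results at 15/30: about 2% false equivalence and 93% to 96% power over the blank rates tried.

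Below the minimum, the child's value is missing and goes to SAP 8.3 and 15.1.2, with the 20% trigger stated as a percentage of children. Report blank nights by arm.

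Add sensitivity analyses scoring blank nights all wet and all dry, because wet/answered is not safe if blanks depend on wetness. At 15/30 and a true 2-night difference, with 15% of dry and 5% of wet nights blank, false equivalence is 6% for wet/answered and 4% for the count. With 15% of wet and 5% of dry nights blank, it is 0.5% and 11%.

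The cost is SAP wording and programming on diary data already collected. Children with sparse diaries become missing: with a minimum of four and 10% blanks, 0.3% of children, or 8% if blanks cluster.

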#### Data collection/Data Sources:

Participants will be assessed on Day 0 (baseline), for demographics, height and weight, medical history, concomitant medication, prior use of absorbent pants/nappies, and full physical examination (optional). In case of remote visit, height and weight and full physical examination will be done when the visit is performed on-site. At Day 28 ± 7days (end of run-in and randomisation), Day 56 ± 7days (end of intervention/core trial period) and Day 84 ± 7 days (end of extension period), participants will be assessed for adverse events (AEs) since the previous visit, concomitant medication used to treat AEs, and patient-reported outcome (PRO) questionnaires. Baseline, randomisation, and any subsequent visit could be performed remotely via phone or video/teleconference, if an on-site visit cannot be performed. For remote visits, PRO questionnaires will be accessed through the parent's/carer's own electronic device and study materials (i.e., DryNites®, bed mats) will be shipped to the patient. The PRO questionnaires will be available after a given visit (and should be completed before the next visit). The PRO questionnaires can also be completed remotely, within the same time window, if completion is not feasible during any on-site visit including baseline. Dry and wet nights will be captured every day from the start of the run-in period to discontinuation of the study through an electronic diary, accessible through the parent's/carer's own device (smart phone, tablet, or computer).

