**Table 1 Study Objectives and Endpoints** 

Objectives	Endpoints
Primary	
To determine if discontinuing the use of DryNites® absorbent pants over a period of 4 weeks has any impact on the rate of spontaneous resolution of NE compared with continuing use of DryNites® absorbent pants	Average number of wet nights in Week 8 (last week of the intervention period)
Secondary	
To determine if using DryNites® absorbent pants improves the child's Quality of Life (QoL) assessed by the Paediatric Incontinence Questionnaire (PinQ) compared with not using absorbent pants	• Change from baseline in total PinQ score at Day 56 ± 7days
To determine if using DryNites® absorbent pants improves the parent/carer's QoL assessed by the World Health Organization Quality of Life BREF (WHOQoL-BREF) compared with not using absorbent pants	• Change from baseline in total score of each domain at Day $56 \pm 7$ days
To determine if using DryNites® absorbent pants improves the child's sleep assessed by the Paediatric Daytime Sleepiness Scale (PDSS) compared with not using absorbent pants	• Change from baseline in total PDSS score at Day 56 ±7 days
To determine if using DryNites® absorbent pants improves the parent/carer's sleep assessed by the Checklist Individual Strength questionnaire (CIS) compared with not using absorbent pants	Change from baseline in subscale scores at Day 56     ±7 days
To determine if DryNites® absorbent pants offer different benefits or limitations to previously used absorbent pants/nappies	Descriptive statistics

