#### 4.3.4. Screen Failures

Screen failures are defined as patients who were consented to participate in the study but are not subsequently randomly assigned to study treatment, for any reason identified before, during, or at the end of the run-in period.

A minimal set of screen failure information is required to ensure transparent reporting of screen failure subjects to meet the Consolidated Standards of Reporting Trials (CONSORT) publishing requirements and to respond to queries from regulatory authorities. Minimal information

includes demographics, screen failure details, eligibility criteria, and any serious adverse event (SAE).

These patients should have the reason for study withdrawal recorded as 'Screen failure'; this reason for study withdrawal is only valid for patients who were not randomised.

Individuals who do not meet the criteria for randomisation in this study may be re-screened one time, after an additional run-in of 1 week.

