7.1 Reference Start Date

Reference start date is defined as the day of the randomisation and will appear in every listing where an assessment date or event date appears.

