7.3 Windowing Conventions

The following table describes assignment of visit windows to the following data for purposes of analysis:

Table A:Windowing

Assigned Study Day (Inclusive)		Visit Assigned	
From	То		
-35	0	Visit 1	
1	1	Visit 2	
2	42	Visit 3	

Template No.: RWI_TP_BIOS0013 Revision 1

Reference: RWI_WI_BIOS0015

Effective Date: 15Jun2018

43 63 Visit 4

To define cut on visits to the patient's diary, visit date will be used as reference along with windowing conventions.

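### The 'Week 4' primary endpoint follows the actual Visit 3 date, so the week counted can be week 2 to week 6 after randomisation; tie it to a fixed set of diary nights.

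*SAP*

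**What the plan says.** SAP 15.1.1 counts the diary's yes answers to the wetting question, "counted over the last 7 days of the intervention period (from randomisation till the Visit 3 day". SAP 15.1 bounds the period in the same way: "last week of the intervention period (lasting from randomisation to Visit 3". SAP 7.3 adds "To define cut on visits to the patient's diary, visit date will be used as reference along with windowing conventions", and its Table A assigns study days 2 to 42 to Visit 3. The SAP's time origin is randomisation (SAP 7.1: "Reference start date is defined as the day of the randomisation").

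The protocol numbers its visits from baseline: "At Day 28 ± 7days (end of run-in and randomisation), Day 56 ± 7days (end of intervention/core trial period" (synopsis, data collection; also section 4.1 and Table 2). Its Table 1 gives the endpoint as "Average number of wet nights in Week 8 (last week of the intervention period", and section 4.5.1 calls the same week Week 4.

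SAP 15.1.2, setting out the imputation model, describes the outcome as "number of wet nights during the last week on the 4 weeks period after randomisation".

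Neither document gives a fixed-night rule or a minimum interval between randomisation and Visit 3.

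**The concern.** The primary objective concerns a 4-week period. Under Protocol 4.7.3 every randomised child was wet on all 7 nights of the last run-in week, so the arms start level and any effect of stopping must develop afterwards. A child counted at week 2 has had half the intended exposure; one counted at week 6 has had half as much again. Calling both Week 4 mixes exposures in the primary comparison.

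The direction matters in an equivalence trial. Early counting tends to bring the arms together, and Protocol 5.4.6 already warns that a short period may produce equivalence simply because neither group changes. The trial is also open-label, so it is better if the endpoint week does not depend on when a family attends.

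A second problem is that SAP 15.1.1 and 15.1.2 describe the same variable differently. If imputation were used, the imputed and the observed values could refer to different weeks.

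**Working it through.** **Inputs.** Visit 2: Day 21 to 35. Visit 3: Day 49 to 63 (protocol windows). Endpoint: the 7 days ending at Visit 3 (SAP 15.1.1). Planning values: wet-night probability 0.95 (continuing) and 0.80 (discontinuing), margin 2/7 (2 nights a week), 15 continuing and 30 discontinuing children (Protocol 5.1 and 5.2).

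**Step 1. The plan's own figures.**
- Nominal interval: 56 − 28 = 28 days, which gives nights 22-28 as intended.
- Stated power at 15/30 is 99%. By normal approximation, SE = √(0.95×0.05/105 + 0.80×0.20/210) = 0.0348, and Φ[(0.2857 − 0.15)/0.0348 − 1.96] = 97.3%. Simulating the protocol's procedure gives 97.7%. With a pooled t-test interval, the kind of analysis SAP 15.1.3 names, it is about 91%. The timing point does not depend on these figures.

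**Step 2. Range of the interval.**
- Shortest: 49 − 35 = 14 days. Longest: 63 − 21 = 42 days.
- If Visit 3 is booked 28 ± 7 days from actual randomisation: 21 to 35 days.
- Re-screening: a child "may be re-screened one time, after an additional run-in of 1 week" (Protocol 4.3.4). If such a child is randomised on Day 35 and seen on the nominal Day 56, the interval is 21 days. The documents do not say whether Day 0 is reset.

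**Step 3. What each interval would read.** Assume the planned gap builds linearly and all children share one interval of T days: gap = 7 × 0.15 × T/28 nights per week. The last column is the simulated chance of concluding equivalence at 15/30 with a pooled t interval.

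| T (days) | Nights counted | Gap (nights/week) | Chance of equivalence |
|---|---|---|---|
| 14 | 8-14 | 0.53 | about 100% |
| 21 | 15-21 | 0.79 | 99.5% |
| 28 | 22-28 | 1.05 | 91.4% |
| 35 | 29-35 | 1.31 | 59.4% |
| 42 | 36-42 | 1.58 | 21.3% |

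Placing the build-up at the middle of the counted week, 7 × 0.15 × (T − 3)/25, gives 0.46, 0.76, 1.05 and 1.64 at 14, 21, 28 and 42 days. The pattern is the same.

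**Step 4. How often the week moves.** Assume both visit dates are uniform and independent over their windows (15 × 15 = 225 combinations):
- exactly 28 days: 15/225 = 6.7%
- no overlap with nights 22-28 (T ≤ 21 or T ≥ 35): 72/225 = 32%; with realised windows of ±5 days 20/121 = 16.5%, with ±3 days 0%
- with Visit 3 uniform over 28 ± 7 days from randomisation: 2/15 = 13%

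**Step 5. Net effect of the mixture.** The interval is symmetric about 28 and the gap is linear in T, so the mean gap is still 1.05. Drawing each child's interval as in Step 4 raises the SD in the discontinuation arm from 1.06 to 1.08 nights. The chance of concluding equivalence goes from 91.4% to 90.2% at 15/30 and from 97.7% to 97.0% at 20/40. It stays above 99.9% at 40/80. The small change is against equivalence.

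**The case against.** The strongest reply is that this is ordinary visit-window noise. The plan describes consecutive 4-week periods and dispenses a 4-week supply at each visit (Protocol 4.4.2): 4 × 10 = 40 or 3 × 13 = 39 pants, which would not cover 42 nights. Intervals of 14 and 42 days need the two visits at opposite ends of their windows. Early and late children largely cancel, as Step 5 shows. Imputation is triggered only at 20% missing data, so the SAP 15.1.2 wording may never come into play.

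Most of this stands as to size. It does not remove the gap: nothing in either document prevents the wider intervals, and booking from actual randomisation would still leave weeks 3 to 5.

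Three stronger readings are tempting, but the documents do not support them.
- *That the endpoint is defined as three different weeks.* Protocol Table 1, Protocol 4.5.1 and SAP 15.1.1 all identify the final week of the intervention period. Only SAP 15.1.2 departs from it.
- *That the SAP's Visit 1 window drops children who had the extra run-in week.* A child randomised on Day 35 has Visit 1 at study day −34 (−35 if there is no day 0), inside Table A's −35 to 0. A miss needs randomisation after Day 35, and Visit 1 does not enter this endpoint.
- *That visit timing biases the arms.* Both arms have the same windows. Arm-dependent attendance is possible in an open-label trial, but nothing shows it.

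**Conclusion.** The concern holds as a defect of definition. The rule as written can label any week from 2 to 6 after randomisation as Week 4 (3 to 5 on the narrower reading), and it disagrees with SAP 15.1.2 whenever Visit 3 is not at 28 days.

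The expected cost is mixed exposure rather than bias: no change in the mean difference and about 1 percentage point in the chance of concluding equivalence at 15/30. This rests on symmetric, independent, uniform visit dates and a linear build-up, none of which the documents state. A reader might infer from the 14-day row of the table that the design leans towards equivalence. That follows only if visits run systematically early; if they ran late, the lean would be the other way. The plan should be changed on this point, but the defect does not by itself undermine the primary analysis.

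**What to change.** - In SAP 15.1.1 and 7.3, define the primary endpoint as wet nights on diary nights 22-28 after randomisation, whatever the Visit 3 date. Each entry describes the previous night, so state which entry is night 1.
- Make SAP 15.1.2 and Protocol Table 1 name that same week.
- Reconcile the visit-timing passages (Protocol synopsis, 4.1, Table 2, 4.7.2 and 4.7.4) so that the diary continues to night 28 when Visit 3 is earlier. At present a child who declines the extension completes the end-of-study form at Visit 3.
- State a rule for diaries that stop before night 28. For example, treat those nights as missing, use the last 7 available nights as a sensitivity analysis, and say how a partly missing week counts towards the 20% imputation trigger.

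**Cost.** SAP wording and a short protocol clarification; the diary is already daily, and power under the planning values is unchanged. The downside is missing endpoint nights for children with an early Visit 3 who decline the extension. This could be more than a handful: with evenly spread visit dates, (225 − 15)/2 = 105 of 225 combinations (47%) put Visit 3 before day 28, and 36/225 (16%) at or before day 21, where the whole endpoint week would fall after Visit 3. Hence the diary continuation and the fallback rule belong to the fix.
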